8.1. Efficacy Assessments

Efficacy will be measured by

- HbA1c
- fasting blood glucose measured by SMBG
- Level 2 and 3 nocturnal hypoglycemia
- Level 2 and 3 hypoglycemia events
- body weight
- insulin dose
- CGM measurements
 - time in range between 70 and 180 mg/dL (3.9 and 10 mmol/L), inclusive
 - glucose variability, and
 - time in hyperglycemia or hypoglycemia, and
- patient-reported outcomes questionnaires
 - TRIM-D
 - SIM-Q
 - SF-36 v2 Health Survey
 - Basal Insulin Experience, and
 - EQ-5D-5L.

See Section 3 for specific efficacy endpoints.

See Section 8.3.6 for information related to hypoglycemia and hyperglycemia.

8.1.1. Glucose Monitoring

Participants **must** use only the study-provided glucometer during the study.

8.1.1.1. Self-Monitoring of Blood Glucose (SMBG)

Glucometer for participant use during the study

Participants will receive a sponsor-approved glucometer and related testing supplies for use during the study.

Site personnel will train the participant on correct use of the glucometer for self-monitoring blood glucose and reporting of hypoglycemia data in the e-diary.

Participants should use the glucometer

- whenever hypoglycemia is experienced or suspected
- when there is awareness of increased risk related to changes in dietary intake, physical activity, or inadvertent or atypical insulin dosing
- to check for hyperglycemic events, or
- as directed by the investigator.

When to measure fasting blood glucose (FBG) during the study

Site personnel will train the participant to measure FBG daily when possible, and a minimum of 3 times per week using the study-provided glucometer.

The FBG should be measured upon waking in the morning, prior to food or caloric beverage intake.

Glucometer data transfer

The study-provided glucometer will wirelessly transmit blood glucose measurements to the participant's e-diary. Site personnel will be able to view SMBG data that have been transmitted to the e-diary through a web-based portal as well as any reported events of hypoglycemia.

8.1.1.2. Continuous Glucose Monitoring (CGM) Systems

The study-provided CGM system or alternative sponsor-approved glucose monitoring device will be used in blinded mode during the study.

The blinded CGM will not display the sensor glucose readings to the participant or investigator, and high and low glucose alerts will not be available to the participant.

Participants are not allowed to use a personal, non-study CGM device during the study.

Training and initiation

Site personnel will dispense CGM supplies and initiate blinded CGM sessions at the times specified according to the SoA. Participants will be trained on the CGM system before use and will be required to replace the sensor at designated intervals per the investigator instruction.

Participants are not allowed to connect the transmitter and/or sensor of the CGM system to a personal smartphone, smartphone application, or other system.

CGM data compliance

At the end of each CGM session, participants will return the CGM system or used sensors to the site. Site personnel will upload the CGM data to a vendor-hosted online portal to view data capture compliance using the available reports and visualization tools. The compliance threshold of 80% for each session is defined as the percentage of actual data versus expected data collected during a session. Site personnel will re-educate participants on CGM operation and requirements when session compliance is <80%.

To minimize data loss, the CGM service vendor will review site uploads and notify site users and/or site monitor when sessions do not meet the compliance thresholds. CGM compliance

reports will also be provided to the Sponsor during the study for review and to determine if further mitigation is necessary.

8.1.2. Patient-Reported Outcomes

The self-administered questionnaires will be translated into the native language of the region and administered at the site during the designated visits in the SoA.

Order of administering the questionnaires during the visit

If the participant is not adversely affected by their fasting condition, the questionnaires should be completed before the participant has discussed their medical condition or progress in the study with the investigator or study personnel.

Preferred administration order of these questionnaires is

1. TRIM-D
2. SIM-Q
3. SF-36 v2 Health Survey Acute Form
4. Basal Insulin Experience: Likelihood of incorporating into routine, and
5. EQ-5D-5L.

8.1.2.1. Treatment-Related Impact Measure – Diabetes (TRIM-D)

Description of TRIM-D

The TRIM-D is a participant self-administered instrument, which assesses the impact of diabetes treatment on participants' functioning and well-being across available diabetes treatments. Participants assess their experience "over the past 2 weeks."

The TRIM-D assesses 5 domains of impact.

Domain	Number of items per domain
Treatment Burden	6
Daily Life	5
Diabetes Management	5
Compliance	4
Psychological Health	8

Scoring

Each of the 28 items is assessed on a 5-point scale, where higher scores indicate a better health state.

8.1.2.2. Simplicity of Diabetes Treatment Questionnaire (SIM-Q) Single Medication Status Version

Description of SIM-Q

The SIM-Q is a brief 10-item measure developed to assess the simplicity and complexity of treatment for T2D. This version of the instrument assesses the simplicity and complexity of a single medication. The participant responses should consider only the assigned study intervention.

In this study, only the last 2 questions of the SIM-Q will be completed

“How simple or complex is your medication treatment for diabetes?” and

“Overall, how simple or complex is it to manage your diabetes, including medication, checking your blood glucose levels, diet, and any other aspects of diabetes treatment?”

Scoring

Each item is scored on a 5-point scale ranging from “Very complex” to “Very simple.”

8.1.2.3. Short Form-36 Version 2 Health Survey Acute Form

Description of SF-36 v2

The SF-36 v2 Health Survey Acute form is a participant self-administered measure designed to assess these 8 domains

- Physical Functioning
- Role Physical
- Bodily Pain
- General Health
- Vitality
- Social Functioning
- Role Emotional, and
- Mental Health.

The Physical Functioning domain assesses limitations due to health “now” while the remaining domains assess functioning “in the past week.” Participants answer each item using Likert 3-point, 5-point, or 6-point scales for the responses.

Scoring

Each domain is scored individually, and information from these 8 domains is further aggregated into 2 health component summary scores, the Physical Component Summary and Mental Component Summary.

Scoring of each domain and both summary scores are norm based and presented in the form of T-scores, with a mean of 50 and standard deviation of 10.

Higher scores indicate better levels of function and/or better health (Maruish 2011).

8.1.2.4. Basal Insulin Experience: Likelihood of Incorporating into Routine

Description of questionnaire

The Basal Insulin Experience: Likelihood of incorporating into routine is a self-reported scale consisting of a single question to understand the participant’s likelihood of incorporating their study insulin into their diabetes management routine.

Scoring

The question is rated on a 5-point scale with responses ranging from “very unlikely” to “very likely.”

8.1.2.5. EQ-5D-5L

Description of EQ-5D-5L

The EQ-5D-5L (EuroQol Research Foundation 2019) is a standardized, 5-item, self-administered instrument for use as a measure of health outcome. It provides a simple descriptive health profile and a single health state index value that can be used in the clinical and economic evaluation of health care as well as population health surveys.

The EQ-5D-5L assesses 5 dimensions of health

- mobility
- self-care
- usual activities
- pain or discomfort, and
- anxiety or depression.

The 5L version scores each dimension at 5 levels

- no problems
- slight problems
- moderate problems
- severe problems, and
- unable to perform or extreme problems.

A total of 3125 health states are possible.

Scoring

The scores on the 5 dimensions can be presented as a health profile or converted to a single health state index value.

The single health state index value can be derived based on a formula that attaches weights to each of the levels in each dimension. This index value ranges between less than 0 to 1, where negative values are valued as worse than dead, 0 is a health state equivalent to death, and 1 represents perfect health.

EQ Visual Analog Scale

The EQ Visual Analog Scale records the respondent's self-rated health status on a vertical graduated visual analog scale from 0 to 100, where 0 represents the worst imaginable health and 100 represents the best imaginable health.

In conjunction with the health state data, this provides a composite picture of the respondent's health status.

8.2. Safety Assessments

Planned time points for all safety assessments are provided in the SoA.

8.2.1. Physical Examinations

Physical examination at screening

The complete physical examination will include, at a minimum, assessments of these systems

- cardiovascular
- respiratory
- gastrointestinal, and
- neurologic.

Height and weight will be measured and recorded.

Additional assessments include clinical signs and symptoms related to T2D, T2D-related illnesses, and injection site reactions.

8.2.2. Vital Signs

Blood pressure and pulse rate will be measured when specified in the SoA and as clinically indicated. Additional vital signs may be measured during study visits if warranted, as determined by the investigator.

8.2.3. Electrocardiograms

Local and single 12-lead ECG will be obtained as outlined in the SoA.

Electrocardiograms will initially be interpreted by the investigator or qualified designee at the site as soon after the time of ECG collection as possible, and ideally while the participant is still present, to determine whether the participant meets entry criteria and for immediate participant management, should any clinically relevant findings be identified.

The investigator or qualified designee is responsible for determining if any change in participant management is needed and must document their review of the ECG printed at the time of evaluation.

8.2.4. Clinical Safety Laboratory Tests

See Section 10.2 for the list of clinical laboratory tests to be performed and the SoA for the timing and frequency.

The investigator must review the laboratory results, document this review, and report any clinically relevant changes occurring during the study as an AE.

The laboratory results must be retained with source documents unless a Source Document Agreement or comparable document cites an electronic location that accommodates the expected retention duration.

Clinically significant abnormal laboratory findings are those which are not associated with the underlying disease, unless judged by the investigator to be more severe than expected for the participant's condition.

All laboratory tests with values considered clinically significantly abnormal during participation in the study or within 5 weeks after the last dose of intervention should be repeated until the values return to normal or baseline or are no longer considered clinically significant by the investigator or medical monitor.

If such values do not return to normal or baseline within a period of time judged reasonable by the investigator, the etiology should be identified and the sponsor notified.

All protocol-required laboratory assessments, as defined in Section 10.2, must be conducted in accordance with the SoA, standard collection requirements, and laboratory manual.

If laboratory values from non-protocol-specified laboratory assessments performed at an investigator-designated local laboratory require a change in participant management or are considered clinically significant by the investigator, for example, SAE or AE or dose modification, then report the information as an AE.

8.2.5. Hepatic Monitoring

Close hepatic monitoring

Initiating laboratory and clinical monitoring for abnormal liver laboratory test results

Laboratory tests, including ALT, AST, ALP, TBL, direct bilirubin, GGT, and creatine kinase, should be repeated within 48 to 72 hours to confirm the abnormality and to determine if it is increasing or decreasing, if 1 or more of these conditions occur. This table shows when to repeat laboratory tests.

If a participant with baseline results of...	develops the following elevations:
ALT or AST <1.5x ULN	ALT or AST \geq 3x ULN
ALP <1.5x ULN	ALP \geq 2x ULN
TBL <1.5x ULN	TBL \geq 2x ULN (except for participants with Gilbert's syndrome)
ALT or AST \geq 1.5x ULN	ALT or AST \geq 2x baseline
ALP \geq 1.5x ULN	ALP \geq 2x baseline
TBL \geq 1.5x ULN	TBL \geq 1.5x baseline (except for participants with Gilbert's syndrome)

What to do if the abnormal condition persists or worsens

If the abnormal liver test result persists or worsens, clinical and laboratory monitoring, and evaluation for possible causes of abnormal liver tests should be initiated by the investigator in consultation with the Lilly-designated medical monitor. At a minimum, this evaluation should include physical examination and a thorough medical history, including

- symptoms
- recent illnesses, for example, heart failure, systemic infection, hypotension, or seizures
- recent travel
- history of concomitant medications, including over-the-counter, herbal and dietary supplements, and
- history of alcohol drinking and other substance abuse.

Frequency of monitoring

Initially, monitoring of symptoms and liver tests should be done 1 to 3 times weekly, based on the participant's clinical condition and liver test results.

Subsequently, the frequency of monitoring may be lowered to once every 1 to 2 weeks, if the participant's clinical condition and laboratory results stabilize.

Monitoring of ALT, AST, ALP, and TBL should continue until levels normalize or return to approximate baseline levels.

Comprehensive hepatic evaluation

When to perform a comprehensive evaluation

A comprehensive evaluation should be performed to search for possible causes of liver injury if 1 or more of the conditions in this table occur.

If a participant with baseline results of...	develops the following elevations:
ALT or AST <1.5x ULN	ALT or AST \geq 3x ULN with hepatic signs or symptoms ^a , or ALT or AST \geq 5x ULN
ALP <1.5x ULN	ALP \geq 3x ULN
TBL <1.5x ULN	TBL \geq 2x ULN (except for participants with Gilbert's syndrome)
ALT or AST \geq 1.5x ULN	ALT or AST \geq 2x baseline with hepatic signs or symptoms ^a , or ALT or AST \geq 3x baseline
ALP \geq 1.5x ULN	ALP \geq 2x baseline
TBL \geq 1.5x ULN	TBL \geq 2x baseline (except for participants with Gilbert's syndrome)

^a Hepatic signs or symptoms are severe fatigue, nausea, vomiting, right upper quadrant abdominal pain, fever, rash, and/or eosinophilia >5%.

What a comprehensive evaluation should include

At a minimum, this evaluation should include

- physical examination and a thorough medical history, as outlined above
- tests for
 - PT-INR
 - viral hepatitis A, B, C, or E, and
 - autoimmune hepatitis, and
- an abdominal imaging study, for example, ultrasound or computed tomography scan.

Based on the patient's history and initial results, further testing should be considered in consultation with the Lilly-designated medical monitor, including tests for

- hepatitis D virus
- cytomegalovirus
- Epstein-Barr virus
- acetaminophen levels
- acetaminophen protein adducts
- urine toxicology screen
- Wilson's disease
- blood alcohol levels

- urinary ethyl glucuronide, and
- blood phosphatidylethanol.

Based on the circumstances and the investigator's assessment of the participant's clinical condition, the investigator should consider referring the participant for a hepatologist or gastroenterologist consultation, magnetic resonance cholangiopancreatography, endoscopic retrograde cholangiopancreatography, cardiac echocardiogram, or a liver biopsy.

Additional hepatic data collection (hepatic safety CRF) in study participants who have abnormal liver tests during the study

Collect additional hepatic safety data collection in the hepatic safety CRFs if a participant develops

- a hepatic event considered to be an SAE, or
- discontinues study intervention due to a hepatic event, or
- has changes in laboratory results described in this table.

If a participant with baseline results of...	develops the following elevations...	Then...
Elevated serum ALT		
ALT <1.5x ULN	ALT to ≥ 5 x ULN on 2 or more consecutive blood tests	Collect additional hepatic safety data in the hepatic safety CRF.
ALT ≥ 1.5 x ULN	ALT ≥ 3 x baseline on 2 or more consecutive blood tests	
Elevated TBL		
TBL <1.5x ULN	TBL ≥ 2 x ULN, except for participants with Gilbert's syndrome	
TBL ≥ 1.5 x ULN	TBL ≥ 2 x baseline	
Elevated ALP		
ALP <1.5x ULN	ALP ≥ 2 x ULN on 2 or more consecutive blood tests	
ALP ≥ 1.5 x ULN	ALP to ≥ 2 x baseline on 2 or more consecutive blood tests	

Note: The interval between the 2 consecutive blood tests should be at least 2 days.

See Section 10.5 for hepatic laboratory tests.

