7.1.1. Liver Chemistry Stopping Criteria

The study intervention should be interrupted or discontinued if 1 or more of these conditions occur.

Elevation	Exception
ALT or AST >8x ULN	
ALT or AST >5x ULN for more than 2 weeks	
ALT or AST >3x ULN and either TBL >2x ULN or INR >1.5	In participants with Gilbert's syndrome, doubling of direct bilirubin should be used for intervention interruption or discontinuation decisions rather than TBL >2x ULN.
ALT or AST >3x ULN with the appearance of fatigue, nausea, vomiting, right upper quadrant pain or tenderness, fever, rash, and/or eosinophilia (>5%)	
ALP >3x ULN, when the source of increased ALP is the liver	
ALP >2.5x ULN and TBL >2x ULN	In participants with Gilbert's syndrome, doubling of direct bilirubin should be used for intervention interruption or discontinuation decisions rather than TBL >2x ULN.
ALP >2.5x ULN with the appearance of fatigue, nausea, vomiting, right upper quadrant pain or tenderness, fever, rash, and/or eosinophilia (>5%)	

Resumption of the study intervention can be considered only in consultation with the Lilly-designated medical monitor and only if the liver test results return to baseline and if a self-limited, non-intervention etiology is identified.

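### With baseline liver tests below 1.5x ULN and an isolated, asymptomatic ALT or AST rise to above 3x and below 5x ULN, no instruction requires the INR on which a Section 7.1.1 stopping criterion turns

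*Protocol*

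**What the plan says.** **Stopping rule.** Protocol Section 7.1.1 lists conditions, any one of which should lead to interruption or discontinuation of study drug. One is "ALT or AST >3x ULN and either TBL >2x ULN or INR >1.5". INR alone can therefore complete it. Separate rows act on ALT or AST alone: above 8x ULN, or "ALT or AST >5x ULN for more than 2 weeks".

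**Monitoring steps in Section 8.2.5.**
- Repeat draw, triggered at ALT or AST of at least 3x ULN when baseline is below 1.5x ULN: "Laboratory tests, including ALT, AST, ALP, TBL, direct bilirubin, GGT, and creatine kinase, should be repeated within 48 to 72 hours".
- If the abnormality persists or worsens, further monitoring and evaluation of causes "should be initiated by the investigator in consultation with the Lilly-designated medical monitor". The stated minimum is an examination and a history.
- Continued monitoring: "Monitoring of ALT, AST, ALP, and TBL should continue until levels normalize or return to approximate baseline levels".
- Full work-up: "A comprehensive evaluation should be performed to search for possible causes of liver injury if 1 or more of the conditions in this table occur". Its minimum content includes PT-INR. For baselines below 1.5x ULN it starts at ALT or AST of at least 5x ULN, at least 3x ULN with hepatic signs or symptoms, TBL of at least 2x ULN (outside Gilbert's syndrome), or ALP of at least 3x ULN.
- Footnote to that table: "Hepatic signs or symptoms are severe fatigue, nausea, vomiting, right upper quadrant abdominal pain, fever, rash, and/or eosinophilia >5" (the last figure is a percentage).

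**Appendix.** Section 8.2.5 closes with "See Section 10.5 for hepatic laboratory tests". Section 10.5 lists PT-INR, but sends the reader back to 8.2.5 for the choice of tests.

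**The concern.** A stopping criterion can be applied only if its inputs are measured. The criterion has two arms, TBL and INR, and both start above 3x ULN. TBL is in the repeat panel and in continued monitoring, so its arm can always be judged. INR is in neither. Between the level where the INR arm begins to apply (above 3x ULN) and the level where INR becomes mandatory without symptoms (5x ULN), the value that decides the rule may never be obtained.

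Take a participant with ALT at 4x ULN, TBL below 2x ULN, no hepatic signs or symptoms, and a true INR above 1.5. This participant meets a stated condition for interrupting drug. A site in full compliance with 8.2.5 need not find that out, and dosing can continue. The stake is individual safety management.

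**Working it through.** The plan states no figure on this point, so there is none to reproduce. The check sets the triggers side by side.

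**Setting.** Baseline ALT/AST, TBL and ALP each below 1.5x ULN; no Gilbert's syndrome; no sign or symptom listed in 7.1.1 or the 8.2.5 footnote; current TBL below 2x and ALP below 3x ULN. Let A be ALT or AST in multiples of ULN.

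**Rules.**
- INR arm of the criterion (7.1.1): A > 3 and INR > 1.5.
- Repeat draw (8.2.5): A ≥ 3.
- Comprehensive evaluation (8.2.5): A ≥ 5, or A ≥ 3 with signs or symptoms, or TBL ≥ 2, or ALP ≥ 3. In this setting only A ≥ 5 remains.
- ALT or AST alone (7.1.1): A > 8, or A > 5 for more than 2 weeks.

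| A (x ULN) | INR arm applies | Repeat draw triggered | PT-INR required | Rule on ALT or AST alone |
|---|---|---|---|---|
| above 3, below 5 | yes | yes | **no** | none |
| 5 to 8 | yes | yes | yes | only if above 5 for more than 2 weeks |
| above 8 | yes | yes | yes | at once |

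In the first row no other 7.1.1 laboratory condition can be met: A is too low for the two ALT/AST rows, and the setting excludes the TBL and ALP rows. In Gilbert's syndrome a doubled direct bilirubin replaces the TBL arm.

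**Grid check.** Five ALT/AST values (3.01, 3.5, 4, 4.5, 4.99), four TBL values (0.5, 1, 1.49, 1.99) and five ALP values (0.5, 1, 2, 2.5, 2.99) give 5 × 4 × 5 = 100 combinations. The comprehensive evaluation is triggered in 0 and the repeat draw in 100. In all 100, an INR of 1.6 would meet 7.1.1. At the edges, A = 5, TBL = 2, ALP = 3, or A = 3.5 with symptoms each trigger the evaluation, so the stated conditions mark the limits of the gap.

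**Other places INR could be required.** The schedule of activities, the Section 10.2 list, the hypersensitivity samples in 10.2.1 and the hepatic CRF rules in 8.2.5 name no INR. SAP Section 4.6.3.2 sets no INR trigger. SAP Appendix 11 gives abnormality levels for prothrombin time, which is not an instruction to collect it.

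**Raised baseline.** For baseline ALT/AST b ≥ 1.5x ULN without symptoms, the repeat starts at 2b and the comprehensive evaluation at 3b. Exclusion criterion 20 removes only ALT or AST above 3x ULN at screening, so such baselines can occur.
- b = 2: repeat at 2 × 2 = 4x ULN, evaluation at 3 × 2 = 6x ULN.
- b = 2.5: repeat at 5x ULN, evaluation at 7.5x ULN.
- 3b exceeds 5 when b > 5/3 ≈ 1.67, and exceeds 8 when b > 8/3 ≈ 2.67. In the latter case the above-8x rule applies first.

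For b above about 1.67, the range without required INR therefore extends past 5x ULN.

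**The case against.** The best defence is that 8.2.5 is a graded design: repeat the chemistry, evaluate with the medical monitor, then do a full work-up with PT-INR. Section 7.1.1 lists conditions to act on and does not promise that each is measured at every elevation. Discretion is also wide. The repeat list is open-ended, Section 10.2 allows additional tests at any time, and Section 8.2.4 asks for the etiology of abnormalities that do not resolve. The investigator may stop drug for safety reasons under 7.1 whatever the INR, and the sponsor's internal team reviews safety continuously (10.1.5.1).

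This limits the size of the point, and that part stands. It does not remove the gap, because each of these routes permits INR and none requires it. The sponsor itself set the INR arm to begin above 3x ULN, not at 5x.

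Two objections to a simple remedy also stand. Anticoagulants are not excluded and 7.1.1 has no exception for them. If INR were required and 7.1.1 left as it is, an anticoagulated participant with ALT 3.5x ULN and INR above 1.5 would meet the stopping rule as written. And one INR at the repeat does not cover a participant who stays at 4x ULN for weeks while INR rises later.

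A reader might infer that the INR arm is inoperative at every level, or that the plan prevents sites from measuring INR. The documents support neither: the comprehensive evaluation requires PT-INR, and discretionary testing is allowed throughout. A reader might equally infer that INR is required from 5x ULN for everyone. That is true only for baseline ALT/AST below 1.5x ULN.

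**Conclusion.** The point holds, with minor severity. In the group defined above, full compliance with 8.2.5 can leave a stated stopping criterion unassessed while ALT or AST is above 3x and below 5x ULN. These are limits on the ALT/AST scale, not shares of participants or of risk. The documents give no frequency, and an INR above 1.5 with TBL below 2x ULN, ALP below 3x ULN and no symptoms is probably uncommon, so few participants are likely to be affected. No efficacy endpoint or error rate is touched.

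The conclusion assumes that an open list requires only what it names, and that the cross-references between 8.2.5 and 10.5 create no trigger of their own. It does not extend to the claim that participants in this range go unmonitored: they have repeat chemistry and, if the abnormality persists, symptom and liver-test monitoring 1 to 3 times weekly at first.

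**What to change.** 1. In Section 8.2.5, add PT-INR to the 48 to 72 hour repeat when ALT or AST triggers that repeat and the value is above 3x ULN. Repeats triggered by ALP or TBL alone do not need it.
2. In the Exception column for the INR criterion in Section 7.1.1, state that in participants taking anticoagulants an INR above 1.5 is interpreted against anticoagulant use or baseline INR, in consultation with the medical monitor.

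In the group described, every value above 3x ULN already triggers the repeat, so no visit or draw is added. The change secures one INR at that draw; later INRs stay with the investigator and the medical monitor. Participants with a raised baseline gain an INR at their existing repeat and no new draw. For them the stretch from 3x ULN up to 2x baseline stays uncovered. Whether those triggers should be aligned with the fixed 3x ULN limit is for the sponsor's hepatic experts, given that non-alcoholic fatty liver disease is eligible.

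**Cost.** Wording in two places of a protocol amendment, with the ethics and, if substantial, health authority approvals described in Section 10.1.1. One extra tube at a draw already required, analysed by the central laboratory as Section 10.5 demands. Some INR results in anticoagulated participants will need interpretation.

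### With raised baseline ALT, AST or ALP, three liver work-up triggers in Protocol 8.2.5 lie above the matching stops in 7.1.1

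*Protocol*

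**What the plan says.** Protocol 8.2.5 has two relevant tables. The first lists the elevations after which liver tests "should be repeated within 48 to 72 hours to confirm the abnormality". The second lists those that call for a comprehensive evaluation (INR, hepatitis tests, abdominal imaging). Both use multiples of ULN when baseline is below 1.5x ULN and multiples of baseline otherwise. The raised-baseline rows are:

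- repeat test: "ALT or AST \geq 2x baseline" and "ALP \geq 2x baseline";
- comprehensive evaluation: "ALT or AST \geq 2x baseline with hepatic signs or symptoms", or "ALT or AST \geq 3x baseline" without symptoms, and ALP again at twice baseline.

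Protocol 7.1.1 interrupts or discontinues study drug at levels fixed in ULN. The relevant ones are "ALT or AST >3x ULN with the appearance of fatigue, nausea, vomiting" (the symptom list continues), "ALT or AST >5x ULN for more than 2 weeks", ALT/AST above 8x, ALP above 3x if the liver is the source, and ALP above 2.5x with symptoms. Two further stops combine ALT/AST above 3x, or ALP above 2.5x, with bilirubin (TBL) above 2x; the ALT/AST one may use INR above 1.5 instead. The only exceptions concern Gilbert's syndrome.

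Criterion 20 in 5.2 allows screening ALT and AST up to 3x, ALP up to 2.5x and TBL up to 2x ULN, and accepts non-alcoholic fatty liver disease. The raised-baseline rows will therefore apply to some eligible participants.

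**The concern.** At baselines below 1.5x ULN, each repeat trigger sits at or below its stop, so confirmation comes first. At raised baselines the repeat and work-up thresholds move up with baseline while the stops stay put, and the order reverses.

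Section 7.1.1 itself orders no tests. A participant could come off drug for a hepatic reason with no confirmatory sample and no search for a cause required by 8.2.5. The sustained 5x stop has a further difficulty: it cannot be judged without a later sample, and near the top of the eligible range 8.2.5 does not ask for one.

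**Working it through.** Let b be baseline in multiples of ULN. A trigger at twice baseline is 2b. For a stop above level S, the uncovered values lie above S and below 2b, so the band has width 2b − S. Eligible ranges from criterion 20: b up to 3.0 for ALT/AST and up to 2.5 for ALP. Other analytes are taken as normal.

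| Pair | S | b = 1.5 | b = 2.0 | b = 2.5 | b = 3.0 |
|---|---|---|---|---|---|
| ALT/AST with symptoms, evaluation | 3 | none | 3.0–4.0 | 3.0–5.0 | 3.0–6.0 |
| ALP (liver source), repeat and evaluation | 3 | none | 3.0–4.0 | 3.0–5.0 | not eligible |
| ALP with symptoms, repeat and evaluation | 2.5 | 2.5–3.0 | 2.5–4.0 | 2.5–5.0 | not eligible |
| ALT/AST, repeat, against the 5x level | 5 | none | none | none | 5.0–6.0 |

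The first three rows contain the three triggers at issue: one for ALT/AST and two for ALP. The ALT/AST repeat row has no symptom version, so I do not count it as a matching pair; it too starts at 2b, so it does not fill the first band.

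The fourth row is the secondary point. 2b exceeds 5 only when b exceeds 2.5: at b = 2.6 the band is 5.0–5.2, at 2.75 it is 5.0–5.5, and at 3.0 its width is 6.0 − 5.0 = 1.0x ULN. The Schedule of Activities has clinical chemistry at Weeks 0, 12, 26, 52 and 57, giving gaps of 12, 14, 26 and 5 weeks. With no unscheduled sample, the worst-case wait is 26 weeks.

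Checks that limit the claim:

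- **Bilirubin stops.** With baseline TBL below 1.5x, the row "TBL \geq 2x ULN (except for participants with" Gilbert's syndrome) is in both tables and fires before TBL passes 2x. No band is left. With baseline TBL at 1.75x, the repeat needs 1.5 × 1.75 = 2.625x and the evaluation 2 × 1.75 = 3.5x. A TBL of 2.1x then meets the stop's bilirubin condition but neither trigger, and ALT/AST from 3 to 2b and ALP from 2.5 to 2b are uncovered.
- **8x stop.** The evaluation at 3b exceeds 8 only when b > 8/3 = 2.67; at b = 3.0 the band is 8.0–9.0. The repeat (2b, at most 6.0) has already fired.
- **Baselines below 1.5x.** The ALP evaluation starts at 3x, which is 0.5x above the 2.5x symptom stop. The repeat, at 2x, comes first.

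**The case against.** The strongest defence is that the protective action is intact. The stops apply whatever 8.2.5 says, and no text requires monitoring triggers to precede them. An absolute ceiling with a baseline-relative work-up is a reasonable choice when fatty liver disease is eligible: a move from 3.0x to 3.05x is hardly a change.

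Other provisions also help. Section 8.2.4 makes the investigator review results, repeat clinically significant values and identify the cause if they do not settle. GGT is in the routine chemistry panel and helps judge whether ALP is of liver origin. Discontinuing drug for a hepatic event triggers the hepatic safety CRF. Resumption requires a return to baseline and an identified cause. Anyone applying the sustained 5x stop must resample.

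Most of this stands, and it keeps the point small. It does not remove it. Section 8.2.4 depends on the investigator judging the value clinically significant, extra tests under Appendix 2 are discretionary, and the resumption conditions matter only if restarting is considered. If the rise is trivial, a repeat is the cheapest way to show that, and 7.1.1 is interrupting the drug at that level anyway.

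A reader might infer that the stops themselves fail, that all of them precede the work-up, or that a 26-week lapse is to be expected. The documents support none of these. The stops are independent of 8.2.5. The bilirubin stops are covered at ordinary TBL baselines. The 26 weeks assumes that a value above 5x is reviewed and not followed up. Nor is the plain ALT/AST repeat row above all its stops: 2b would exceed 8x only at b above 4, outside the eligible range.

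**Conclusion.** The point holds as a safety-consistency gap, of optional severity. For ALT/AST baselines above 1.5x up to 3x ULN, and ALP baselines above 1.5x up to 2.5x ULN, three 8.2.5 triggers lie above their matching stops. The excess is at most 3.0x ULN for symptomatic ALT/AST and at most 2.0x for ALP (2.5x against the symptom stop). The sustained 5x gap is secondary, at most 1.0x ULN wide.

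The consequence is late or unrequired confirmation and work-up, not a missing stop. The primary analysis is unaffected, liver injury is not among the potential risks listed in 2.3.1, and the documents do not say how many participants have raised baselines.

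The sizes assume that baseline stays within the screening limits. Section 8.2.5 does not define baseline. SAP 4.1 uses the last value up to first dose, and chemistry is drawn again at Visit 3. If 8.2.5 means that value, b could be higher: at an illustrative b of 3.5 the secondary band would be 5.0–7.0x.

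**What to change.** Leave criterion 20, 7.1.1 and the existing tables as they are, and add one rule to 8.2.5: regardless of baseline, repeat the liver tests within 48 to 72 hours and perform the comprehensive evaluation whenever any 7.1.1 criterion is met, and repeat the liver tests whenever ALT or AST exceeds 5x ULN.

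The trigger then fires no later than the stop, so each band above closes, including the symptomatic ALP gap at baselines below 1.5x and the raised-TBL cases. A value above 5x that persists would enter the monitoring that 8.2.5 already sets at one to three times weekly, which supplies the later sample. For ALP above 3x the rule takes effect once the source is judged hepatic.

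The cost is one added rule and a few extra repeat tests and work-ups, almost all in participants already meeting a stop.
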